Cover Page

Document type: Study protocol and Statistical Analysis Plan

Study title: Single Shot Lumbar Erector Spinae Plane (ESP) Block in Total Hip Replacement (THR)

NCT number: NCT04388553

Document date: 10 Dec 2020

Glossary of Terms (in alphabetical order)

ANZCA - Australian and New Zealand College of Anesthetists
ASA - American Society of Anesthesiologists
BMI - body mass index
CI - confidence interval
CONSORT - Consolidated Standards of Reporting Trials
ESP - erector spinae plane
ESPB - erector spinae plane block
GA - general anesthesia
MRC - Medical Research Council
NRS - numeric rating scale
OR - odds ratio
PCA - patient controlled analgesia
POD1 - first postoperative day
Prn - pro re nata
SD - standard deviation
THR - total hip replacement

INTRODUCTION

Total hip replacement (THR) improves quality of life in pathologies like osteoarthritis, rheumatoid arthritis and avascular necrosis¹. Postoperative complications, for instance, venous thromboembolism and chest infection may be prevented by early mobilization which is facilitated by effective pain management^{2,3}.

Multimodal analgesia is applied to these patients, with a combination of opioid and non-opioid oral analgesics and regional block. Each of the components has its own limitations; for opioid, postoperative nausea and vomiting and respiratory depression restrict its use; non-steroidal anti-inflammatory drugs are contraindicated in those with renal impairment; and adjuvants like gabapentinoid can lead to dizziness and sedation in some patients. Regional techniques like femoral nerve block, lumbar plexus block and epidural anesthesia have shortcomings like incomplete coverage of nerves innervating the hip joint, limb weakness, invasiveness of the procedure and/or potential hemodynamic instability. Newer plane blocks like Pericapsular Nerve Group block⁴ and Supra-inguinal Fascia Iliaca block⁵ are emerging as candidates for analgesia after THR. Erector spinae plane block (ESPB) has been described in hip surgery by Tulgar in a case report⁶. However, the evidence of lumbar ESPB was limited mainly to case reports at the time of this study being designed. We postulated that compared to no block, a single shot lumbar ESPB at L1 would reduce postoperative fentanyl use and postoperative pain scores (primary outcomes) in a multicenter, double-blinded, randomized clinical trial in patients undergoing unilateral THR.

METHODS

This was a multicenter, double-blinded, randomized (with a randomization ratio of 1:1), controlled, parallel-group study conducted in Hong Kong. The study was carried out from July 2020 to November 2021 in two tertiary centers, which were situated in New Territories West and had an annual caseload of around 450 total joint replacements. Patients were counselled on the potential risks of general anesthesia (GA) and ESPB during the pre-anesthetic assessment, after which written informed consent would be obtained if they agreed to be recruited. This study was approved by the New Territories West Cluster Research Ethics Committee (reference number: NTWC/REC/20007), and was registered prior to patient enrollment at ClinicalTrials.gov (NCT04388553, Principal investigator: [name], Link to registration page: <https://clinicaltrials.gov/ct2/show/NCT04388553>, Date of registration: May 14, 2020). The full trial protocol can also be accessed via ClinicalTrials.gov. This manuscript was constructed in the format suggested by the Consolidated Standards of Reporting Trials (CONSORT) guideline⁷.

Eligibility criteria

To be eligible for the study, patient must be above 18 years old, under American Society of Anesthesiologists (ASA) class 1-3 and underwent primary elective unilateral THR. They should understand and accept the risks for GA and ESPB. They should also be able to use postoperative patient-controlled analgesia (PCA) and express their pain intensity in Numeric Rating Scale (NRS).

Patients with the following conditions were excluded from this study: 1) emergency case, 2) bilateral THR, 3) revision THR, 4) THR done under neuraxial technique, 5) contraindication for ESPB (i.e. patient refusal, mentally incapacitated, injection site infection, local spine pathology or surgery, coagulopathy with International Normalized Ratio > 1.4 or thrombocytopenia < 75 x 10⁹/L), 6) regular strong opioid (e.g. fentanyl, morphine, oxycodone, methadone, heroin etc.), 7) severe obstructive sleep apnea syndrome (Apnea-Hypopnea Index ≥ 30), 8) severe obesity (Body Mass Index (BMI) ≥ 35).

Randomization

Simple randomization method was employed. Allocation concealment was achieved by drawing randomly from a set of sealed opaque envelopes with allocation inside on the day before surgery, followed by attaching it to the pre-anesthetic assessment form by the investigator. The envelope was opened by the attending anesthetist after the patient was put under GA to ensure patient blinding. If the operation was cancelled or the patient could not use PCA postoperatively, for instance, postoperative mechanical ventilation or delirium, the envelope would be put back into the pool. A CONSORT diagram illustrates the participant flow (Figure 1).

Intervention

After the patient was put under GA (maintained with nitrous oxide and either sevoflurane or desflurane), the envelope was opened. For the treatment arm, lumbar ESPB was performed by 4 designated anesthetists. For the control arm, no injection was performed and a plaster was applied to the target skin puncture site to blind the assessor. A curved probe (Fujifilm Sonosite Edge (Washington, United States); 2-5 MHz) was placed sagittally on the flank to look for the 12th rib, which was traced medially to the transverse process of the T12. The probe was then moved one spinal level caudad to locate the L1 vertebra with the L1 transverse process in the middle of the probe. A 10 cm Pajunk Sonoplex® needle (Geisingen, Germany) was inserted in an in-plane manner to aim at the tip of the L1 transverse process. After hitting the bone, 0.5-1ml normal saline was used for hydrolocating the plane between the erector spinae muscle and the transverse process beneath it. Forty mL of 0.25% levobupivacaine (or a maximum of 2mg/kg body weight made up to the same volume) was injected into the ESP. After the block, the injection site was also covered with a plaster like the control arm. If the block was technically challenging and the anatomy was difficult to identify, the procedure would be aborted and the patient would be excluded from the study with the assignment envelope returned. After the injection, the surgeon was instructed not to infiltrate any local anesthetics into the wound. Intraoperatively, both arms received intravenous fentanyl (4 µg/kg in the first hour, 2 µg/kg in the second hour and then 1 µg/kg/hour onward) as the only analgesic and 4mg intravenous ondansetron was given. Patients from both arms were prescribed intravenous PCA fentanyl as the first-line analgesia with the following setting for at least 24 hours postoperatively: 1) bolus dose of 40% of the corrected body weight in µg fentanyl (ideal body weight in kg = body height in cm -105 (female) or -100 (male), corrected body weight = (total body weight - ideal body weight) x 0.4 + ideal body weight); 2) no background infusion; 3) lock-out time of 6 minutes; and 4) 1 hour limit of 120 - 200 µg (to be decided by the attending anesthetist). Preoperative regular oral analgesics (paracetamol 0.5 - 4 g daily, non-steroidal anti-inflammatory drugs like ibuprofen 200 - 400 mg daily or diclofenac 25 - 100 mg daily, tramadol 50 - 200 mg daily and gabapentinoids like gabapentin 100 - 900 mg daily or pregabalin 25 - 150 mg daily) were continued postoperatively unless contraindicated. Oral tramadol 50mg was prescribed as the rescue analgesic and intravenous metoclopramide 10mg was prescribed as the rescue antiemetic. Patients were instructed to request prn tramadol from ward nurse if pain control was inadequate despite intravenous fentanyl PCA.

Outcome assessment

Patients were followed up on POD1 by independent assessors from the acute pain service team consisting of a nurse and an anesthetist, who were not involved in the intraoperative care of the patient and was blinded by being instructed not to look at the anesthetic record. The primary outcomes, namely the amounts of PCA fentanyl used 12-hour and 24-hour postoperatively (in µg) and the pain intensity at rest and on movement on POD1, were assessed. NRS with a scale from 0 to 10 was adopted for pain assessment. NRS 0 means no pain while NRS 10 means the worst pain experienced⁸. The secondary outcomes were the rates of postoperative nausea (defined as feeling of having an urge to vomit)⁹ and postoperative vomiting (defined as forcing the contents of the

stomach up through the oesophagus and out of the mouth)⁹ from the end of operation till the follow-up on POD1 as recalled by the patient, the need of rescue antiemetic and analgesia in the first 24 hours postoperatively, along with knee flexion power of the operated limb in Medical Research Council (MRC) scale. The oral morphine equivalents of fentanyl and prn tramadol used at 12 hours and 24 hours postoperatively were calculated according to the opioid conversion table from the Faculty of Pain Medicine of Australian and New Zealand College of Anaesthetists (ANZCA)¹⁰. Of note, the use of antiemetic was not a surrogate of postoperative nausea or vomiting.

Statistical analysis

The data were collected by the investigator and analyzed by SPSS® 26 package. Per-protocol analysis was planned because it reflects treatment efficacy better, and any patient who deviated from the protocol (for instance, technically challenging block, postoperative mechanical ventilation and delirium) would not be analyzed. Since data of the primary outcomes, the oral morphine equivalents and the knee flexion power were not normally distributed as evidenced by skewed appearance of the histograms and p values of Shapiro-Wilk test smaller than 0.05, we used Mann-Whitney U test to compare these outcomes between treatment group and control group, while the Hodges-Lehmann estimator was employed to compute the median difference and the 95% confidence interval (CI). The proportions of postoperative nausea, postoperative vomiting and need of rescue antiemetic between two arms were compared by Chi-square test, whereas the proportions of those requiring rescue analgesia between both groups were analyzed by 2-sided Fisher's exact test (due to presence of expected count less than 5). Multivariable regression would be employed to adjust the outcomes should there be any major discrepancy (absolute standardized difference > 0.46 with n=35 in both groups as suggested by Austin¹¹) in the perioperative factors between treatment and control groups.

Sample size estimation

A pilot study was done by retrospectively examining cases of primary unilateral THR in the two tertiary centers from January to December 2019 with postoperative PCA (infusion-plus-bolus and bolus only). The mean fentanyl use upon follow-up on the first day postoperatively (POD1) without regional block (including femoral nerve block/fascia iliaca block/lumbar plexus block/lateral cutaneous femoral nerve block/gluteal nerve block) or local anesthetics infiltration (n=36) was 664 µg, whereas that with regional block or local anesthetics infiltration (n=20) was 368 µg. To detect a reduction of fentanyl use by 300 µg which was comparable to data from the pilot study (Standard Deviation (SD) 438 µg), along with a reduction in pain score (in NRS) by 2 points (SD 2.42 for rest pain and 2.48 for movement pain) on POD1, a sample size of 35 patients was required for both treatment and control arm ($\kappa = 1$) with type 1 error (α) of 0.05 and power ($1-\beta$) of 80% in two-sample t-test assuming equal variance and normality of data distribution¹². Secondary outcomes were not taken in account of sample size calculation, and were considered to be exploratory only. No interim analysis was planned.

REFERENCES

1. Świtoń A, Wodka-Natkanięc E, Niedźwiedzki Ł, Gaździk T, Niedźwiedzki T. Activity and Quality of Life after Total Hip Arthroplasty. *Ortop Traumatol Rehabil.* 2017;19(5):441-450.

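### Opened allocation envelopes are returned for re-use and the patients dropped; for aborted blocks this can happen only in the block arm, so the draws are not simple 1:1 randomization and the analysed arms are not the randomized arms

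*Combined protocol and SAP*

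**What the plan says.** The Methods section states a 1:1 ratio, and the Randomization section says: "Simple randomization method was employed". The mechanism is "drawing randomly from a set of sealed opaque envelopes with allocation inside on the day before surgery". The size and composition of that set are not given. On timing, the Randomization section says: "The envelope was opened by the attending anesthetist after the patient was put under GA".

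Two rules send envelopes back:

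- **Randomization section.** If the operation is cancelled, or the patient cannot use PCA afterwards (ventilation and delirium are the examples given), "the envelope would be put back into the pool".
- **Intervention section.** If the block is technically challenging and the anatomy hard to identify, "the procedure would be aborted and the patient would be excluded from the study with the assignment envelope returned".

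The Intervention section also says that controls receive a plaster and no injection. The Statistical analysis section plans a per-protocol analysis and adds that "any patient who deviated from the protocol (for instance, technically challenging block, postoperative mechanical ventilation and delirium) would not be analyzed". No as-allocated analysis is stated.

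**The concern.** Simple randomization at 1:1 means that each patient's allocation is an independent draw with probability one half. Here envelopes come from a set, used ones stay out, and some come back because of what happened to a patient after allocation. Later allocation probabilities then depend on earlier patients' post-allocation events.

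The more serious matter is who is removed. A block can be aborted only in a patient allocated to block. A control with equally difficult anatomy is never identified and stays in. The comparison becomes block patients with feasible anatomy against controls of every kind, and randomization no longer guarantees that the two are alike. If anatomy that is hard to block goes with different fentanyl use or pain, part of any observed difference is selection.

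Inability to use PCA can occur in either arm, but it arises after treatment, so removal on that ground is not guaranteed to be balanced either. Return of a still-sealed envelope after a cancelled operation is not at issue.

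**Working it through.** **Inputs from the Sample size estimation section:** 35 per arm, target difference 300 µg, SD 438 µg, α = 0.05 (taken as two-sided), power 80%, two-sample t-test.

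**Inputs assumed, because the documents give neither:** abort rate p = 5%, 10% or 20%; difference D in mean fentanyl use between hard- and easy-to-block patients = 0.25 to 1 SD, that is 0.25 × 438 = 110 µg to 438 µg, of either sign.

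**1. The plan's own figure.** The normal approximation gives n = 2 × (1.960 + 0.842)² × (438/300)² = 33.5, so 34 per arm. The t-test calculation gives 34.45, so 35, with 80.6% power at 35. The stated 35 reproduces and is not in dispute.

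**2. Allocation.** Under simple randomization of 70 patients, an exact 35:35 split has probability 9.5%, and the 95% range for one arm is 27 to 43. A fixed set used up without replacement behaves differently. As an example, assume a set of 35 block and 35 control envelopes. After one block envelope is drawn, the next draw has a block probability of 34/69 = 49.3% if that envelope stays out and 35/70 = 50% if it is returned. Filling 35 analysed block patients takes 35/(1 − p) opened block envelopes, against 35 for control when aborted blocks are the only losses.

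**3. Selection bias.** The expected number of hard-to-block patients is 35p among controls and 0 in the analysed block arm. The spurious difference in means is p × D. The standard error of the difference is 438 × √(2/35) = 104.7 µg. With no true block effect, the rejection rate follows from the noncentral t distribution with noncentrality pD/104.7.

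| Assumed p | Opened block envelopes (share of all opened) | Hard-to-block controls | Spurious difference, D = 0.25 to 1 SD | Share of 300 µg | Type I error, D = 0.25 to 1 SD |
|---|---|---|---|---|---|
| 5% | 36.8 (51%) | 1.75 | 5.5 to 21.9 µg | 2 to 7% | 5.0 to 5.5% |
| 10% | 38.9 (53%) | 3.5 | 11.0 to 43.8 µg | 4 to 15% | 5.1 to 7.0% |
| 20% | 43.8 (56%) | 7 | 21.9 to 87.6 µg | 7 to 29% | 5.5 to 13.1% |

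A simulation that modelled the controls as a mixture of easy and hard patients gave 12.5% in the last cell at 1 SD, consistent with the 13.1%.

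**4. Cost of analysing as allocated.** If aborted patients gain nothing from allocation to block, the expected effect is 300 × (1 − p).

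| Assumed p | Effect | Power at 35 per arm | Per arm for 80% power |
|---|---|---|---|
| 0 | 300 µg | 80.6% | 35 |
| 5% | 285 µg | 76.5% | 39 |
| 10% | 270 µg | 72.0% | 43 |
| 20% | 240 µg | 61.8% | 54 |

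**The case against.** The strongest reply is that the effect is probably small. Local spine pathology or surgery and BMI of 35 or more are excluded before the draw. Four designated anesthetists do the blocks, and the trigger for aborting is narrow. A 20% abort rate is then a stress case, and the 13.1% needs that rate together with a full 1 SD difference. At 10% aborted and 0.5 SD, type I error is 5.5%. The abort decision also precedes any postoperative outcome, so the outcome does not drive it. All of this stands as a limit on size. It does not remove the asymmetry, because anatomy fixed before surgery can still be related to pain and opioid use.

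The per-protocol analysis was declared in advance, with the reason that it better reflects efficacy. That is openly stated, but the reason does not address an exclusion that only one arm can undergo, nor does it justify re-using the allocation. The planned regression adjustment does not help either: it is triggered by imbalance in perioperative factors, and no assessment of block feasibility is described for controls.

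The participant flow diagram is not available in the text reviewed and may list these patients. Listing them would answer the point about concealed losses but would not return them to the analysis. Resealing may likewise be implied; the text does not describe it. The misnaming of the randomization method, taken alone, is mainly a labelling fault.

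Finally, the type I error and power figures are for a t-test, whereas the Statistical analysis section specifies the Mann-Whitney test for skewed data. They show orders of magnitude only.

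**Conclusion.** The concern holds. Two things follow from the text without any assumption: the described procedure is not simple 1:1 randomization, and patients are removed after allocation for a reason that can arise in the block arm only. The direction of the resulting bias is unknown. Its size rests wholly on the assumed abort rate and on the assumed difference between hard- and easy-to-block patients. Within the ranges used it runs from negligible (5 µg) to nearly a third of the target effect (88 µg). The upper figures are not strict bounds, since they depend on capping the difference at 1 SD. The point must be fixed even if the bias proves small, because nothing in the stated analysis lets a reader recover the randomized comparison. The sample size of 35 per arm is unaffected as a calculation.

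**What to change.** 1. Use a pre-generated list, prepared by someone who does not enrol patients, with sequentially numbered opaque envelopes taken in order. An unrestricted 1:1 list would match the stated method.
2. Allow an envelope to be withdrawn only while unopened, and log it. Once opened, the allocation belongs to that patient and is not re-used.
3. Follow patients with aborted blocks, and other post-opening exclusions, wherever outcomes can be obtained. Analyse them as allocated, at least alongside the per-protocol analysis.
4. Report every opened and every returned envelope by arm and reason.
5. Correct the description of the randomization method.

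The document describes conduct in the past tense, so items 1 and 2 cannot reach allocations already made; items 3 to 5 still apply. Item 3 depends on whether POD1 data exist for the excluded patients, which the documents do not say. If they do not, that should be stated and the number reported by arm. The clinical decision to abort a block is left as it is.

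The cost is a list, numbered envelopes, a log, POD1 data on a few more patients, and wording. There are two drawbacks. Under an unrestricted list the arms may differ by a few patients. The as-allocated effect is also diluted: at 10% aborted, power falls from 81% to 72%, and about 43 per arm would restore 80%; at 5% aborted the figures are 77% and 39 per arm.

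### The anesthetist who opens the envelope also chooses the PCA 1-hour limit, with no requirement to choose before the arm is known: a small, avoidable bias route into PCA fentanyl use

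*Combined protocol and SAP*

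**What the plan says.** Under METHODS, Randomization: "The envelope was opened by the attending anesthetist after the patient was put under GA to ensure patient blinding". From that moment the attending anesthetist knows the arm.

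Under Intervention, the PCA bolus follows a body-weight formula, the lock-out is 6 minutes, and there is "no background infusion". The remaining setting, the 1-hour limit, may lie anywhere from 120 to 200 µg, "to be decided by the attending anesthetist". No rule for the choice is given, nor when it is made. A rescue route exists: "Patients were instructed to request prn tramadol from ward nurse if pain control was inadequate despite intravenous fentanyl PCA".

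Under Outcome assessment, the primary outcomes include "the amounts of PCA fentanyl used 12-hour and 24-hour postoperatively", together with pain at rest and on movement on the first postoperative day (POD1). Follow-up is by "independent assessors from the acute pain service team consisting of a nurse and an anesthetist", who took no part in the intraoperative care and were told not to read the anesthetic record.

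Under Statistical analysis, the fentanyl outcomes are compared by Mann-Whitney test with a Hodges-Lehmann difference. "Multivariable regression would be employed to adjust the outcomes should there be any major discrepancy" between arms in perioperative factors, with the threshold at an absolute standardized difference of 0.46. The PCA limit is not named among those factors.

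**The concern.** Blinding is described for the patient and for the POD1 assessors. Neither sets the pump. The clinician who does set its one discretionary value may already know the arm, and that value is a ceiling on what the pump delivers.

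If block patients tended to get lower limits, their recorded fentanyl could fall with no analgesic effect behind it. The reverse tendency would dilute a real effect. A low limit that binds could also raise pain scores and tramadol requests in the same patients, which would partly expose it. Two of the four primary outcomes are directly affected.

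**Working it through.** **Planning figure.** Sample size estimation gives a target of 300 µg, SD 438 µg, α 0.05 (taken as two-sided) and power 80%. Normal approximation: n = 2 × (1.960 + 0.842)² × 438² / 300² = 33.5, so 34 per arm. The exact t-test gives 34.45, so 35 per arm, as stated. That figure is not in dispute.

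**Can the limit bind?** The bolus is 0.4 µg per kg of corrected weight. At an assumed 55 kg it is 22 µg. Ten boluses an hour (6-minute lock-out) would allow 220 µg. A 120 µg limit allows 5 whole boluses (110 µg) and a 200 µg limit allows 9 (198 µg). In a high-demand hour the limit, not the lock-out, is therefore the ceiling.

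**How often?** The pilot mean without block was 664 µg, read here as 24-hour use. Spread evenly, that is 664/24 = 28 µg per hour, and two SDs above the mean is (664 + 2 × 438)/24 = 64 µg per hour. Both are well under 110. The ceiling matters only if demand is concentrated early. With a share f of demand in hours 1-4, a mean patient needs 664 × f/4 per hour: 50 µg at f = 30%, 83 µg at 50% and 116 µg at 70%. Only the last exceeds 110.

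**Size under the extreme choice.** Simulation assumptions:
- every block patient is capped at 110 µg per hour, every control at 198 µg, and the block has no effect;
- 24-hour demand is gamma with mean 664 and SD 438 µg;
- a share f falls evenly in hours 1-4 and the rest evenly over 20 hours;
- a share c of demand above the cap moves to the next hour and the rest is lost;
- there are 35 patients per arm.

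The documents give no value for weight, f or c, so a range is shown.

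| f | c | Mean difference, 24 h (µg) | Hodges-Lehmann shift, 24 h (µg) | False positives, 24 h | False positives, 12 h |
|---|---|---|---|---|---|
| 30% | 0 | 6 | about 0-2 | about 5% | about 5-6% |
| 50% | 0 | 42 | about 14-18 | about 5-6% | about 5-6% |
| 50% | 80% | 22 | below the row above | about 5-6% | about 5-6% |
| 70% | 0 | 94 | about 62-65 | 12.8% | 20.0% |
| 70% | 80% | 51 | about 25 | 5.9% | 6.7% |
| 70% | 100% | under 1 | about 0 | 4.8% | 4.8% |

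The Hodges-Lehmann column is the one to read, because it is the planned estimate. The cap clips only high users, so the mean exaggerates the effect.

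**Less extreme inputs.** With 75% of block patients and 25% of controls at the low limit, f = 70% and c = 0, false positives are 6.8% (24 h) and 8.6% (12 h). With half the pilot demand (mean 332, SD 219 µg, assumed) and a full split, the 24-hour mean difference is at most 12 µg and false positives are 4.4-5.4% for every f and c.

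**The case against.** The strongest reply is that this is an inference from silence about a bounded safety setting. The text does not say when the limit was chosen, a blinded patient presses the button, and blinded staff collect the outcomes. The worrying cell needs a complete split by arm, very early demand and permanently lost unmet demand, and the documents support none of these. Demand itself may be overstated: the pilot mixed infusion-plus-bolus with bolus-only PCA, whereas this trial has no background infusion. The weight-based intraoperative fentanyl given to both arms, which the model omits, may also blunt early demand. All of this stands and is why the point is graded low.

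A second reply is that the planned regression would catch a material imbalance. For a two-level limit, a 75%/25% split has a standardized difference of 0.50/√(0.75 × 0.25) = 1.15, well above 0.46. The largest split that escapes is about 61%/39%: 0.22/√(0.61 × 0.39) = 0.45. At f = 70% and c = 0, false positives are then about 5.5% (24 h) and 6.1% (12 h). This stands in part. It holds only if the limit is recorded and counted as a perioperative factor, which the plan does not say. A complete split could not be adjusted for, because it would coincide with arm.

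A reader might go further and infer that limits were set by arm, or that about a third of the target effect (94/300) could be spurious. The documents support neither. They report no limits by arm, and 94 µg is a mean difference in the most extreme case, not the planned estimate.

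**Conclusion.** The gap is real: the plan gives one role both knowledge of the arm and the only discretionary pump setting, with no order between the two. It is a missing safeguard, not evidence of bias, and the direction of any bias is undetermined.

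Under moderate assumptions the effect on the planned analysis is close to nil. It becomes noticeable only when 70% of demand falls in the first 4 hours, limits split almost completely by arm and much unmet demand is lost; even then the shift is about 65 µg at most. These sizes rest on the assumed weight, demand pattern and carry-over. At f = 70% and c = 0, assumed weights of 45 to 75 kg give 24-hour mean differences of 65 to 95 µg. This is a cheap improvement and not a threat to the trial.

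**What to change.** Have the attending anesthetist enter each patient's limit, within 120-200 µg, on the pre-anesthetic assessment form before the envelope is opened. The envelope is already attached to that form. Alternatively, remove the discretion with one fixed value or a weight-based rule in the same range.

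Allow a later change only for a documented safety reason. It should not be made by the POD1 assessors for that patient, since the decision could draw them to the anesthetic record they are told to avoid. Report initial and changed limits by arm. If recruitment is already over, reporting any recorded limits by arm is still useful.

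The cost is one protocol sentence and one form field, with no extra staff and no change to sample size or analysis. The downside is slightly less freedom to tailor the limit to intraoperative events; urgent safety changes remain possible.

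### Four primary outcomes are tested separately at 5%, and the plan has no success rule, lead outcome or test order

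*Combined protocol and SAP*

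**What the plan says.** Outcome assessment names four primary outcomes in one sentence: "The primary outcomes, namely the amounts of PCA fentanyl used 12-hour and 24-hour postoperatively" "and the pain intensity at rest and on movement on POD1, were assessed". The Introduction also labels both fentanyl use and pain scores as primary.

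Statistical analysis gives one method for all of them: "we used Mann-Whitney U test to compare these outcomes between treatment group and control group". Each gets a Hodges-Lehmann median difference with a 95% confidence interval. The section gives no alpha adjustment, test order, lead outcome or rule for combining results. It already describes the observed data: non-normality is stated "as evidenced by skewed appearance of the histograms and p values of Shapiro-Wilk test smaller than 0.05".

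Sample size estimation states one alpha (0.05) and one power (80%) for a 300 µg reduction in fentanyl, "along with a reduction in pain score (in NRS) by 2 points", and concludes that "a sample size of 35 patients was required for both treatment and control arm". It gives no effect or SD for 12-hour fentanyl. Only the other tier of outcomes is set aside: "Secondary outcomes were not taken in account of sample size calculation, and were considered to be exploratory only". That leaves all four primaries confirmatory.

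**The concern.** With four confirmatory tests, the conclusion depends on how their results are combined. Suppose 12-hour fentanyl is lower in the block arm and pain is unchanged. The trial is positive if any one outcome suffices and negative if all are required. The plan does not say which applies, so the choice can be made after the results are known.

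The rule also decides what the stated 5% and 80% mean for the trial as a whole. Under an any-one rule the 5% no longer describes the chance of a false positive trial. Under an all-required rule the 80% no longer describes the chance of a successful one.

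**Working it through.** **Inputs.** From Sample size estimation: fentanyl difference 300 µg, SD 438 µg; pain difference 2 points, SD 2.42 (rest) and 2.48 (movement); alpha 0.05; power 80%; 35 per arm; two-sample t-test. Sidedness is not stated. A one-sided test would need 27 per arm for fentanyl, so 35 implies two-sided.

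**Assumed, because the documents give no figures.** The correlation between outcomes is taken as a common value from 0 to 0.9. The 12-hour standardised fentanyl effect is set equal to the 24-hour one. The POD1 fentanyl inputs are applied to 24-hour fentanyl.

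**1. Reproduce the plan's figure.** By the normal approximation, n per arm = 2 × (1.960 + 0.842)² × (SD/difference)².

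- Fentanyl: 2 × 7.849 × (438/300)² = 33.5, so 34. By the t-test 34.4, so 35, which is the stated figure.
- Rest pain: 2 × 7.849 × (2.42/2)² = 23.0. By the t-test 24.
- Movement pain: 2 × 7.849 × (2.48/2)² = 24.1, so 25. By the t-test 26.

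Fentanyl sets the sample size. At 35 per arm, t-test power is 80.6%, 92.6% and 91.4% respectively.

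**2. Trial-level figures at 35 per arm, each test at two-sided 0.05.** If the outcomes were independent, family-wise error would be 1 − 0.95⁴ = 18.5%, and joint power would be 0.806 × 0.806 × 0.926 × 0.914 = 55%. For correlated outcomes the figures come from simulating normal data (60,000 replicates per scenario with t-tests; 20,000 for Mann-Whitney).

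| Common correlation | 0 | 0.3 | 0.5 | 0.7 | 0.9 |
|---|---|---|---|---|---|
| Any one suffices: family-wise error, % | 18.5 | 17.5 | 15.7 | 13.3 | 9.4 |
| Of which false claims of benefit, % | 9.7 | 8.8 | 7.9 | 6.6 | 4.5 |
| Any one suffices: power, % | >99.9 | 99.6 | 98.8 | 97.4 | 94.9 |
| All four required: type I error if no effect is real, % | 0.00 | 0.03 | 0.14 | 0.61 | 1.86 |
| All four required: joint power, t-test, % | 54.7 | 61.1 | 65.1 | 70.0 | 75.2 |
| All four required: joint power, Mann-Whitney, % | 50.8 | 57.0 | 61.4 | 66.7 | 72.4 |

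The benchmark for the benefit row is 2.5%, the rate for a single two-sided test in one direction.

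Under the all-required rule, type I error is bounded at 5% whatever the true effects. For example, it is 2.5–3.1% if only rest pain has no effect. Joint power for the three sized outcomes alone is 67.8% to 79.5%.

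**3. Structured correlation.** A common correlation is a simplification: 12-hour fentanyl is part of the 24-hour total, and the two pain scores come from the same follow-up. With assumed correlations of 0.8–0.9 for the fentanyl pair, 0.6–0.8 for the pain pair and 0.2–0.5 across pairs, family-wise error is about 13–16% and joint power about 65–70%.

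**4. Weaker 12-hour effect.** If its standardised effect were 75% or 50% of the 24-hour one, joint power would be 39–56% or 20–29%. These fractions are illustrations and have no source in the documents.

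**5. Lead outcome.** With 24-hour fentanyl as the lead there is one test at 0.05 with 80.6% power, so both stated figures hold by t-test.

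**6. Holm across the four.** The ordered p-values are compared with 0.05/4 = 0.0125, 0.05/3 = 0.0167, 0.05/2 = 0.025 and 0.05. Simulated family-wise error is 4.9% (correlation 0) to 2.7% (0.9). At the strictest step, fentanyl power is 61.9%.

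**The case against.** The strongest defence is that the wording points to an all-required rule. The Introduction joins fentanyl use and pain scores with *and*, and the sample size section adds pain with *along with*. Under that rule there is no type I inflation. The wording does lean that way, but it states a hypothesis and a planning target, not a decision rule. If it were the rule, joint power for all four would be below 80% at every correlation examined.

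A second defence is that fentanyl is listed first and sets the sample size, so it leads in practice. No section says so, and fentanyl is itself split into two primary outcomes.

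Three points against a harsher criticism stand:

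- A reader might infer that both the 5% and the 80% fail for the trial. The documents do not support that. Each fails only under a different rule, and neither fails if 24-hour fentanyl leads.
- A reader might take 18.5% as the trial's error rate. It requires four independent outcomes, which these are not, and it counts false findings of harm. False claims of benefit run at about 5–10%.
- A reader might infer that the sample size is wrong. The arithmetic is right for each endpoint that was sized.

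**Conclusion.** The point holds as a missing decision rule, not as a wrong calculation. Four confirmatory outcomes are tested separately at 0.05, and nothing in the plan says how they combine.

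- **Any one suffices:** family-wise error is about 9–18.5% (about 13–16% under the structured correlations), with about 5–10% for false claims of benefit against 2.5%. Power is ample.
- **All four required:** type I error is at or below 5%, but joint power is about 55–75% by t-test, or about 51–72% by the planned Mann-Whitney test.
- **24-hour fentanyl leads:** 5% and 80% both hold by t-test.

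The per-endpoint sizing and the absence of a rule are certain from the text. The trial-level ranges rest on assumed correlations, normal data and, for joint power, a 12-hour standardised effect equal to the 24-hour one. The documents do not show that any rule was chosen after seeing the results. They show only that nothing written prevents it.

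**What to change.** State the rule in Statistical analysis. As the plan stands, with four primaries and no all-required rule, apply Holm across the four at two-sided 0.05. Report adjusted and unadjusted p-values, and label the 95% confidence intervals as unadjusted.

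If an all-required rule, or a lead outcome with a fixed test order, was documented before unblinding, state and use that instead. The all-required rule needs no alpha adjustment, but the reduced joint power should be disclosed.

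In every case:

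- say that 5% and 80% are per-endpoint planning figures for POD1 fentanyl and pain;
- say that 12-hour fentanyl was not sized;
- label as post hoc any rule, Holm included, that was not documented before unblinding. The section already describes the observed distributions, so a rule written now cannot be presented as prespecified.

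**Cost.** The change needs wording and a recalculation from the four p-values, with no extra patients. Under Holm, 24-hour fentanyl power falls from 81% to about 73–76% if all four effects are real, and to about 64–65% if only the two fentanyl effects are. Power for at least one outcome is about 85–99% in the first case and 69–85% in the second. Under the all-required rule, 80% joint power would have needed about 39–49 per arm (correlation 0.9 to 0) instead of 35.
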